### **6.3.3 Hepatotoxicity**

If the ALT reproducibly (within one week) increases to  $\geq 5$ -times the baseline value, valganciclovir will be held until ALT falls to  $\leq 2$ -times the baseline value, at which time valganciclovir will be restarted. If the ALT again increases  $\geq 5$ -times the baseline value, study drug will be discontinued.

## **6.4 Accountability Procedures for the Study Intervention/Investigational Product(s)**

After receipt of the study product, the site principal investigator (PI) is responsible for study product distribution and disposition and has ultimate responsibility for study product accountability. The Site PI will delegate to the site Research Pharmacist the responsibility for study product accountability. The site pharmacist will dispense valganciclovir in its original bottle and distribute it to the PI (or designee) or to the patient's parent or legal guardian. Each pharmacist will be responsible for and maintain logs of receipt, accountability, dispensation, storage conditions, and disposal of study drug. All study product, whether administered or not, must be documented on the appropriate study product accountability record or dispensing log. Parents/guardians will be instructed to return used bottles to the PI each month. At study completion, the sites will be required to return the drug accountability log to the UAB Central Unit upon request, retaining a copy of the drug accountability form in their study files.

Used and unused study product will be retained at the site until monitored and released for disposition as applicable.

- Upon release for disposition, used or partially used study product will be disposed of by the local site pharmacy in accordance with local regulations.
- Upon completion or termination of the study and after the final monitoring visit, final disposition of the unused study product will be determined by DMID and communicated to the UAB central unit by the DMID Clinical Project Manager for the study. Specifically, all

---

unopened study drug either will be returned to the Clinical Agents Repository (CAR) from the local site pharmacy or destroyed at the site in accordance with local regulations following the direction from the UAB Central Unit or its designee.

## **6.5 Assessment of Subject Compliance with Study Intervention/Investigational Product**

Assessment of compliance with administration of study medication throughout the 4 month treatment period will be achieved by utilization of a medication diary. The parent(s) or legal guardian(s) will complete this diary on a daily basis, indicating the time of drug administration and whether the subject vomited following the dose. The diary will be collected at each study visit, and a new diary provided at that time.

## **6.6 Concomitant Medications/Treatments**

### **6.6.1 Concomitant Medication Assessment**

All concomitant medications will be recorded at each study visit throughout the 4 month treatment period. Administration of any medications will be documented in the subject's source documentation and reported on the subject's electronic case report form (eCRF). Concomitant medications will include all medications, vitamins, and supplements taken within the 4 month study treatment schedule.

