considering similar legislation in their 2015 legislative sessions. This type of “targeted screening” for congenital CMV infection will not identify the overwhelming majority of at-risk neonates, since only 25% of babies with asymptomatic congenital CMV who ultimately develop CMV-associated SNHL have hearing loss present in the first month of life (with the remaining 75% developing hearing loss in later months or the first few years of life). However, targeted screening portends universal screening for congenital CMV infection, as has recently been recommended by a Consensus Conference of leading world experts who gathered before the 5th International Congenital CMV Conference in Brisbane, Australia, on April 19, 2015. A similar staged implementation was seen in the 1990s with hearing screening, whereby testing newborns for hearing abnormalities began in a targeted fashion and only later expanded to universal hearing screening for all babies born in the United States. Once asymptomatic babies are identified through targeted or universal screening programs, there will be tremendous pressure on the managing physician to “do something,” which inevitably will mean treating with oral valganciclovir. Therefore, the window of time to assess the benefit, if any, versus the risk in the asymptotically infected congenital CMV population is narrow. Failure to establish the estimates of clinical effectiveness and to define the risks from treatment now could lead to widespread treatment outside of the confines of a clinical trial, thereby putting babies treated in such a manner at risk of harm with no opportunity to assess for evidence of benefit.

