### **3.2.3 Exploratory Outcome Measures**

- Change in whole blood and plasma CMV viral load through Study Month 6
- Correlation of change in whole blood and plasma CMV viral load with change in hearing at Study Months 4, 6, 12, and 18.
- Correlation of change in urine CMV viral load with change in hearing at Study Months 4, 6, 12, and 18.
- Correlation of development of ganciclovir resistance in differing body compartments (blood, urine, saliva) with change in hearing at Study Months 4, 6, 12, and 18.
- Emergence and kinetics of ganciclovir resistance in differing body compartments (blood, urine, saliva) during antiviral therapy (Study Month 4), and following cessation of antiviral treatment (Study Months 5 and 6)

---

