### **6.6.2 Prohibited Therapies**

Use of the following concomitant medications during the time of administration of antiviral medication in this clinical trial will not be allowed:

- Cidofovir
- Foscarnet
- Probenecid
- Zidovudine
- Didanosine
- Mycophenolate mofetil
- Other Investigational drugs, including but not limited to brincidofovir, maribavir, or letermovir

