### **7.3.10 Study Month 4 ( $\pm$ 10 days, unless alternative window is specified)**

- Obtain 0.5 mL of blood for hematology safety labs
  - WBC count with differential
  - Hemoglobin concentration

- 
- Platelet count
  - Obtain 1.0 mL of blood for chemistry safety labs
    - Alanine aminotransferase (ALT)
    - Direct bilirubin
    - Serum creatinine
  - Measure growth parameters
    - Length in centimeters
    - Weight in kilograms
    - Head circumference in centimeters
  - Review of adverse events and serious adverse events
  - Record concomitant medications
  - Obtain a new hearing assessment or record results from clinically obtained hearing assessment (Window: -10 to +30 days)
    - BSER (to assess neuro-otologic status) and OAEs (DPOAE or TEOAE) will be obtained. If the BSER is abnormal, then bone conduction will be obtained to distinguish between sensorineural hearing loss, conductive loss, or mixed loss. If the OAEs are abnormal, then acoustic immittance measures (tympanometry and acoustic reflexes) will be obtained to better define the middle or inner ear abnormality (e.g., otitis media).
  - Obtain 0.7 mL of blood for CMV viral load
    - Urine collection by bagged specimen (if obtainable) and saliva collected by buccal swab will be attempted on Study Month 4. If urine is obtainable, it will be frozen and sent to the Central Unit Central Laboratory for processing. If urine is not obtainable, a note will be made on the CRF but a protocol deviation will not be reported.
  - Obtain any updated results from etiological investigations for SNHL
  - Collect medication diary

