Approximately 229 subjects with asymptomatic congenital CMV infection without SNHL will be identified and offered enrollment in order to meet the sample size requirements of 176 evaluable subjects. A recent NIDCD study designed to develop screening methodologies for detection of congenital CMV infection (the CHIMES Study, PI: [name], who is a co-investigator in this trial) determined that 0.5% of neonates born in the United States have congenital CMV infection, although higher rates of 0.6% to 1.0% were seen in southern states. Additionally, CHIMES data also suggest that 4.9% of neonates with asymptomatic congenital CMV infection will have baseline SNHL and 95.1% will have normal hearing at birth ([name], personal communication). Therefore, to detect 229 neonates with asymptomatic congenital CMV infection without baseline SNHL to offer enrollment in this trial, an anticipated 48,250 babies will be screened for congenital CMV infection by buccal saliva swab PCR, the high sensitivity of which (97.4%) was recently reported by the CHIMES investigators. A *screening* informed consent form will be utilized for permission to conduct the screening test. Of these 48,250 infants, we anticipate that 241 (0.5%) will have asymptomatic congenital CMV infection. This is a conservative estimate, since we have selected study sites that are in regions of the country where congenital CMV incidence rates are in the 0.6% to 1.0% range. Babies screening positive for congenital CMV infection will have sensorineural hearing testing performed, as is standard of care for babies identified as being congenitally infected with CMV. A second saliva sample and a urine sample will be collected by study personnel (which will be covered by the *screening* informed consent) for confirmatory PCR testing. The likelihood of a false-positive screening test is < 0.03%, but performing a confirmatory test ensures that only those babies truly infected with CMV will be exposed to valganciclovir. We estimate that 12 patients (4.9% of 241) will have baseline SNHL, and that 229 patients (95.1% of 241) will have normal hearing. These approximately 229 asymptotically infected neonates without sensorineural hearing loss will be assessed for all inclusion criteria, and offered enrollment on the treatment portion of the trial if they meet all inclusion criteria and no exclusion criteria. The approximately 12 patients identified as being asymptotically congenitally infected with CMV and with SNHL very likely will be treated clinically with 6 months of oral valganciclovir. If

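### Anti-CMV drugs given after Month 4 are not systematically recorded, although Month 6–18 hearing and Month 5–6 virology are read as results of a 4-month course that has ended

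*Combined protocol and SAP*

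**What the plan says.** - **Recording.** Section 6.6.1: "All concomitant medications will be recorded at each study visit throughout the 4 month treatment period". It also fixes the definition: "Concomitant medications will include all medications, vitamins, and supplements taken within the 4 month study treatment schedule".
- **Visit lists.** The Month 4 list (Section 7.3.10) includes "Record concomitant medications". The lists for Months 5, 6, 12 and 18 (Sections 7.3.11 to 7.3.13 and 7.4.1) do not. The medication diary is last collected at Month 4.
- **Restriction.** Section 6.6.2: "Use of the following concomitant medications during the time of administration of antiviral medication in this clinical trial will not be allowed". The list that follows names neither ganciclovir nor valganciclovir, and nothing in it reaches beyond the treatment period.
- **What is read after Month 4.** Sections 3.1 and 3.2 place SNHL at Month 6 (primary) and at Months 12 and 18 (secondary), after 4 months of drug. Section 3.2.3 describes resistance "following cessation of antiviral treatment (Study Months 5 and 6".
- **Analysis.** Section 11.4.1.2 defines the per-protocol population by completion of four months of drug. Sections 11.4.4 and 11.4.5 say nothing about anti-CMV treatment after that.

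**The concern.** Each result after Month 4 is described as following a fixed 4-month course. If some infants receive more of the same drug from their own physicians, the hearing result belongs to four months plus an unrecorded extension, and a Month 5 or 6 sample may be on drug when it is summarised as off drug. The plan provides no data item that would separate these cases.

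If later drug protects hearing, the error would favour the 4-month course. The Month 6 definition requires SNHL to be present at that visit, so a loss prevented or reversed by unrecorded drug would drop out of the count. Rebound in viral load would look smaller than it is, and resistance that arose on drug could be reported as arising after it. A main analysis that counts every infant regardless of later treatment is legitimate, but even then a reader needs to know how much later treatment there was.

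**Working it through.** **Step 1. Set the collection rule beside the outcomes.** Months after planned stop = visit month − 4.

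| Visit | Months after planned stop | Concomitant-drug item | Result read there |
|---|---|---|---|
| 4 | 0 | yes | SNHL (secondary), virology |
| 5 | 1 | no | viral load, resistance |
| 6 | 2 | no | SNHL (primary), viral load, resistance |
| 12 | 8 | no | SNHL and its degree |
| 18 | 14 | no | SNHL and its degree |

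The Month 6 hearing window runs to +30 days, so exposure before the primary reading is about two months, or three at most for an on-time stop. Months 5 and 6 are 2 of the 13 viral-load time points modelled in Section 11.4.4.

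**Step 2. Reproduce the plan's bounds.** The one-sided 95% Clopper-Pearson upper bound is the 0.95 quantile of Beta(x+1, n−x). At n = 176:
- x = 0: 1.69% (Table 3: 1.69%)
- x = 1: 2.67% (Table 3: 2.67%)
- x = 2: 3.53% (Table 3: 3.50%; a small difference that changes nothing here, since both exceed 3.18%)

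The enrolment cascade also reproduces: 229 × 0.95 × 0.90 × 0.90 = 176.2.

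**Step 3. How fragile is the primary reading?** The bound is below 3.18% only with 0 or 1 case. At the historical rate 176 × 0.0318 = 5.6 cases are expected. If the true count after four months alone were 2, one case hidden by later drug would change the reading.

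**Step 4. Illustrate the primary endpoint.** No rate of later use is given, so the inputs here are assumptions. Suppose the 4-month course alone leaves the rate at p = 3.18%. The chance of a favourable reading is P(X ≤ 1) = (1−p)^176 + 176p(1−p)^175 = 2.3%. If a fraction f of Month 6 cases were hidden by later drug, p becomes 0.0318 × (1−f):

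| f | P(X ≤ 1) |
|---|---|
| 0 | 2.3% |
| 10% | 3.7% |
| 20% | 6.0% |
| 30% | 9.5% |

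In terms of uptake c with half of users' cases prevented, f = 0.5c. Then c = 10% gives 2.9% and c = 30% gives 4.7%. These are upper limits for the stated uptake, because they treat all Month 6 risk as arising after Month 4.

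**Step 5. Illustrate the virology.** Assume a fraction c of infants is back on drug, their virus is fully suppressed, and they would otherwise have rebounded like the rest. The observed mean log10 rebound is (1−c) times the true one. With c assumed at 5% to 20% (11 to 44 of 218 enrolled), it is understated by 5% to 20%.

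**The case against.** The documents do not predict re-treatment of trial infants. A reader might infer from Section 2.2 that the protocol itself regards later valganciclovir as certain, since it says "which inevitably will mean treating with oral valganciclovir". That sentence begins "Once asymptomatic babies are identified through targeted or universal screening programs, there will be tremendous pressure on the managing physician" and concerns babies found by screening programs and treated outside any trial. It says nothing about infants who have finished the study course.

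A reader might also infer from Section 11.2 that nearly every infant with newly found loss would be treated again, because it says of infants with SNHL that they "very likely will be treated clinically with 6 months of oral valganciclovir". Those are the roughly 12 infants with loss at baseline, who enter the observational substudy and have had no study drug. They are indirect support at best. The 6-month recommendation cited in Section 2.1 is for symptomatic disease, and Section 2.2 gives possible liver toxicity beyond four months as a reason for the shorter course.

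The primary endpoint is also lightly exposed. Loss found at Month 4 precedes any treatment it prompts, is counted in the Month 4 secondary outcome, and still counts at Month 6 if present. At 3.18%, 218 infants yield about 6.9 cases by Month 6, so wide uptake would need extension in infants without loss, for which there is no evidence. Even 20% uptake with risk halved lowers 3.18% by at most 0.1 × 3.18 = 0.32 percentage points. The virology outcomes are exploratory.

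Finally, adverse-event review at Month 5 or a viral-load result might reveal later use by chance. The text reviewed holds only the footnotes of Appendix B, and the eCRF and Manual of Procedures were not available.

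Most of this stands and limits the size of the point. It does not remove the gap: Section 6.6.1 states a recording period that ends with treatment, and the visit lists agree with it. Chance discovery is not systematic capture.

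**Conclusion.** A cheap improvement. Anti-CMV drug use after Month 4 is not systematically captured, and no rule says how later hearing and virology data are handled when it occurs. The size of the resulting bias is unknown because the documents give no rate; the percentages above rest on assumed uptake and effect.

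The exposure is ordered by time off study drug: modest for the Month 6 primary endpoint, and greater for hearing and its degree at Months 12 and 18, where 8 and 14 months pass without a question. The Month 5–6 virology is exposed directly, because its interpretation depends on the infant being off drug. The modest primary exposure still deserves attention because the comparison with 3.18% depends on one case. It would go too far to call the later results contaminated: the documents show that such use could go unrecorded, not that it will happen.

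**What to change.** - **Collect.** In Section 6.6.1 and the Month 5, 6, 12 and 18 visit lists, record any systemic anti-CMV drug (drug, start and stop dates, reason) through Month 18.
- **Hearing.** In Section 11.4.4, keep all infants in the main analyses and add a sensitivity display of SNHL proportions with recipients of later antivirals identified. Read it descriptively, because infants with hearing loss may be the ones treated.
- **Virology.** Label Month 5–6 viral-load and resistance samples as on or off drug by actual dates, and report those summaries with and without on-drug samples. Dropping such samples from the main summary would condition on an event after treatment that may be linked to hearing or viral load, so the restricted summary should stand beside the full one and not replace it.

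The cost is one eCRF item at four existing visits, slight site burden and an extra display. No visit, sample or infant is added, and no stated sample-size figure changes. The change neither permits nor forbids later treatment.

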### **6.6.2 Prohibited Therapies**

Use of the following concomitant medications during the time of administration of antiviral medication in this clinical trial will not be allowed:

- Cidofovir
- Foscarnet
- Probenecid
- Zidovudine
- Didanosine
- Mycophenolate mofetil
- Other Investigational drugs, including but not limited to brincidofovir, maribavir, or letermovir

### **6.6.3 Drug Interactions**

In pharmacokinetic studies, the concomitant use of ganciclovir and didanosine (ddI) has been associated with increases in ddI concentrations of greater than 100%. Accordingly, the possibility of increased ddI toxicity should be considered in patients receiving both medications. Coadministration of trimethoprim with oral ganciclovir in adults statistically significantly decreased the renal clearance of ganciclovir by 16.3%, and this was associated with a statistically significant decrease in the terminal elimination rate and corresponding increase in half-life by 15%. However, these changes are unlikely to be clinically significant, as the AUC0-8 and Cmax

were unaffected. The only statistically significant change in trimethoprim pharmacokinetic parameters when coadministered with ganciclovir was a 12% increase in  $C_{min}$ . However, this is unlikely to be of clinical significance and no dose adjustment is recommended.

---

## 7 STUDY SCHEDULE

### 7.1 Screening

It is anticipated that screening of neonates will occur at most sites within the first 2 days of life, prior to discharge from the birth hospital. A *screening* informed consent form will be utilized for permission to conduct the screening test, which consists of obtaining a swab of the buccal mucosa for saliva PCR for CMV DNA. Babies screening positive for congenital CMV infection will have sensorineural hearing testing performed, as is standard of care for babies identified as being congenitally infected with CMV. A second saliva sample and a urine sample will be collected by study personnel (which will be covered by the *screening* informed consent) for confirmatory PCR testing. The likelihood of a false-positive screening test is < 0.03%, but performing a confirmatory test ensures that only those babies truly infected with CMV will be exposed to valganciclovir.

Sensorineural hearing testing will consist of a BSER (to assess neuro-otologic status) and OAEs (DPOAE or TEOAE). If the BSER is abnormal, then bone conduction will be obtained to distinguish between sensorineural hearing loss, conductive loss, or mixed loss. If the OAEs are abnormal, then acoustic immittance measures (tympanometry and acoustic reflexes) will be obtained to better define the middle or inner ear abnormality (e.g., otitis media).

Neonates who screen positive for CMV DNA on their confirmatory PCR testing and who do not have sensorineural hearing loss (SNHL) will be offered enrollment in the treatment portion of the study if they meet all inclusion criteria and do not meet any exclusion criteria.

Neonates who screen positive for CMV DNA on their confirmatory PCR testing and who have SNHL will be offered enrollment into an observational substudy if they are being treated clinically with valganciclovir and meet all inclusion criteria and no exclusion criteria. For this group with SNHL at baseline, all clinical audiologic and safety data will be redacted without alteration from the clinical medical record to the study case report forms. The only research laboratory samples that will be obtained are the whole blood, plasma, urine, and saliva specimens for viral load determination (see Footnote ‘m’ in the Schedule of Events, Appendix B); viral loads would not be routinely followed as part of clinical management (and thus will be study procedures), whereas the valganciclovir treatment and associated safety labs as well as the serial hearing testing are part of clinical care for these patients. Blood for CMV viral load will only be obtained at a given study visit if other blood is being obtained by venipuncture for clinical purposes. Non-study clinical and laboratory assessments that are not performed according to the intervals and listings in Appendix B (Schedule of Events) will not be assessed as protocol deviations, nor will failure to obtain the virology specimen if a venipuncture is not performed as part of clinical care at a given study visit. An *observational* informed consent signed by the neonate’s parent(s) or guardian(s) must be signed prior to enrollment into the observational substudy. The *observational* consent will be signed following the confirmatory PCR testing for CMV DNA and prior to or on Day 1.

---

## 7.2 Enrollment/Baseline

### 7.2.1 Study Day 1 Assessment (Study Day -3 through Study Day 1, unless alternative window is specified)

- After reviewing inclusion/exclusion criteria for treatment portion of the study, confirm that the *treatment* informed consent from parent or legally authorized representative has been signed; *treatment* informed consent will be obtained prior to starting any subject-related assessments or study drug administration.
- Document baseline demographics and clinical assessments
  - Date of birth
  - Gender
  - Race
  - Ethnicity
  - Birth weight
  - Length at birth, if available
  - Head circumference at birth, if available
  - Gestational age at birth
  - Medical history and baseline conditions prior to study enrollment, by body system
- Obtain 0.5 mL of blood for hematology safety labs
  - WBC count with differential
  - Hemoglobin concentration
  - Platelet count
- Obtain 1.0 mL of blood for chemistry safety labs
  - Alanine aminotransferase (ALT)
  - Direct bilirubin
  - Serum creatinine
- Measure growth parameters
  - Length in centimeters
  - Weight in kilograms
  - Head circumference in centimeters
- Review of adverse events and serious adverse events (for Adverse Events that occur following the first dose of study medication)
- Record concomitant medications
- Obtain 0.7 mL of blood for CMV viral load
  - Urine collection by bagged specimen (if obtainable) and saliva collected by buccal swab will be attempted on Study Day 1 (window: Study Day -3 to Study Day 7 for whole blood and urine; and Study Day -30 to Study Day 7 for saliva). If urine is obtainable, it will be frozen and sent to the Central Unit Central Laboratory for processing. If urine is not obtainable, a note will be made on the CRF but a protocol deviation will not be reported.
- Medication diary will be distributed and parent or legal guardian will be instructed on its use.

---

## 7.2.2 Study Day 1

- The first dose of study drug will be administered (and this day will be known as **Study Day 1**)

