After obtaining *treatment* informed consent, enrolled subjects will be treated for four months with oral valganciclovir (16 mg/kg/dose, administered two times per day). **Study Day 1** is the day that the first dose of study medication is administered. Audiologic assessments will be made during the Screening Period and Study Months 4 (end of treatment), 6, 12, and 18. A single, independent study audiologist will assess the audiology test battery for each subject and assign each ear the classifications of normal hearing, mild hearing loss, moderate hearing loss, severe hearing loss, or profound hearing loss based upon their hearing thresholds (in decibels). If a study subject proceeds to cochlear implantation during the course of the study, he/she will not require additional study-related hearing assessments following the implantation procedure but will continue with all other study-related assessments.

Treated infants will be followed for safety throughout the first 6 months of the study (including for 2 months post-treatment). Hematology safety laboratory assessments will be obtained weekly for the first six weeks of study drug administration, then every other week for the next six weeks of study drug administration, and then at months 4 and 5. Chemistry safety laboratory

---

assessments will be obtained every other week for the first 12 weeks (3 months) of treatment, and then at months 4, 5, and 6. Adverse events will be assessed at each study visit during treatment, and at month 5.

Whole blood viral load and plasma viral load will be obtained at each study visit during the course of study drug administration, and then at Study Months 5 and 6. Specimens from subjects with increasing viral loads despite antiviral therapy may be evaluated for ganciclovir resistance by molecular methodologies (e.g., deep sequencing, Sanger sequencing, PCR). Urine and saliva will be obtained at Baseline and Study Months 4, 5, and 6 in order to obtain viral isolates to assist in detection of antiviral resistance.

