## **6.2 Dosage, Preparation and Administration of Study Intervention/Investigational Product**

### **6.2.1 Dosage**

Valganciclovir should be dosed at 16 mg/kg body weight, unless specific dosage adjustment conditions (e.g., renal function) have been met, administered orally twice daily for 4 months. Specific dosing volumes will be provided for each subject. Dose modifications for neutropenia, thrombocytopenia, and hepatotoxicity are detailed in Section 6.3.

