## 7.3 Follow-up

### 7.3.1 Study Day 7 ( $\pm 2$ days)

- Obtain 0.5 mL of blood for hematology safety labs
  - WBC count with differential
  - Hemoglobin concentration
  - Platelet count
- Measure growth parameters
  - Length in centimeters
  - Weight in kilograms
  - Head circumference in centimeters
- Review of adverse events and serious adverse events
- Record concomitant medications
- Obtain 0.7 mL of blood for CMV viral load
- Obtain any updated results from etiological investigations for SNHL
- Collect medication diary, and distribute new one
- Adjust dose of study medication for weight change, if needed

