- n) In addition to whole blood for CMV viral load, urine collection by bagged specimen and saliva collected by buccal swab will be attempted on Study Day 1 (Window: Study Day -3 to Study Day 7 for whole blood and urine; and Study Day -30 to Study Day 7 for saliva). If urine is obtainable, it will be frozen and sent to the Central Unit Central Laboratory for processing. If urine is not obtainable, a protocol deviation will not be reported.
- o) In addition to whole blood for CMV viral load, urine collection by bagged specimen and saliva collected by buccal swab will be attempted on Study Month 4 (Window:  $\pm$  10 days), Study Month 5 (Window:  $\pm$  10 days), and Study Month 6 (Window:  $\pm$  10 days). If urine is obtainable, it will be frozen and sent to the Central Unit Central Laboratory for processing. If urine is not obtainable, a protocol deviation will not be reported.
- p) Valganciclovir administration begins on **Study Day 1**; drug should be administered within 49 days of reconstitution. Study medication diary will be collected and distributed at each study visit throughout the treatment period.

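### The Study Day 1 viral-load window runs to Study Day 7, so an on-drug sample can serve as baseline for the exploratory blood, plasma and urine viral-load change outcomes

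*Combined protocol and SAP*

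**What the plan says.** - **First dose.** Section 4 states that Study Day 1 "is the day that the first dose of study medication is administered". Section 6.2.1 has the drug "administered orally twice daily for 4 months".
- **Default window.** The heading of section 7.2.1 sets the Day 1 assessments at "Study Day -3 through Study Day 1, unless alternative window is specified". Virology has such an alternative: "Study Day -3 to Study Day 7 for whole blood and urine", and "Study Day -30 to Study Day 7 for saliva".
- **Repeated.** Footnote n to the Schedule of Events (Appendix B) gives the same rule: "Window: Study Day -3 to Study Day 7 for whole blood and urine". It is not an isolated slip.
- **Plasma.** Footnote l shows that plasma and whole-blood PCR share one blood sample, so the whole-blood window governs both.
- **Pre-dose rule.** Footnote e requires the neutrophil count before the first dose. No such rule is given for viral load.
- **Day 7 visit.** Section 7.3.1 allows 2 days either side (Days 5 to 9) and takes its own viral-load sample.
- **Outcomes.** Section 3.2.3 lists "Change in whole blood and plasma CMV viral load through Study Month 6", and correlations of change in whole-blood, plasma and urine load with change in hearing. All are exploratory.
- **Analysis.** Section 11.4.4 models log10 whole-blood and plasma load with time as a continuous variable. It does not say whether time is the nominal visit or the actual sampling day, and it does not define baseline viral load.

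**The concern.** A baseline should be free of the treatment whose effect is measured against it. Here the plan's own rule admits an on-treatment sample. If viral load falls in the first days of dosing, an infant with a late baseline shows a smaller fall than really occurred. A mixture of pre-dose and post-dose baselines also adds error to any change score set against hearing.

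Late baselines may not occur at random. Section 8.2 puts virology last when blood volume is short and, in that case, does not count a missed virology sample as a deviation. A catch-up draw within the window would then come after dosing. That is an inference; the documents do not say how often it would happen.

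The overlap with the Day 7 visit adds a bookkeeping question. Nothing says how a single blood draw on Days 5 to 7 should be assigned, and no minimum gap between the two samples is set.

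**Working it through.** **1. The plan's count of time points.** Viral-load visits in section 7 are Days 1, 7, 14, 21, 28, 35, 42, 56, 70 and 84 (10) and Months 4, 5 and 6 (3). 10 + 3 = 13, or 12 degrees of freedom with discrete time. This matches section 11.4.4.

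**2. Time on drug at the end of the window.** Study Day 7 − Study Day 1 = 6 days. At two doses a day that is about 2 × 6 = 12 doses.

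**3. Overlap.** The Day 1 window (Days −3 to 7) and the Day 7 window (Days 5 to 9) share Days 5, 6 and 7. If one draw were the only sample for both visits, the infant would have 13 − 1 = 12 distinct samples. With a pre-dose rule there would be no overlap.

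**4. Size for a simple change score.** The documents give no decline rate and no share of infants affected; both are assumed below.

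Understatement per infant sampled on Day 7 = rate per week × 6/7. Mean understatement = that value × share of infants sampled on Day 7.

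| Assumed fall (log10/week) | Per infant (log10) | Fold | Mean, 10% affected | Mean, 25% | Mean, 50% |
|---|---|---|---|---|---|
| 0.10 | 0.086 | 1.22 | 0.009 | 0.021 | 0.043 |
| 0.25 | 0.214 | 1.64 | 0.021 | 0.054 | 0.107 |
| 0.50 | 0.429 | 2.68 | 0.043 | 0.107 | 0.214 |
| 1.00 | 0.857 | 7.20 | 0.086 | 0.214 | 0.429 |

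These are upper cases for each rate and share, because every late sample is placed on Day 7. A Day 5 sample loses 4/7 of a week's fall instead of 6/7.

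**5. Blood under a continuous-time curve.** A noise-free cubic was fitted to a linear fall over the first 6 weeks followed by a plateau, with half of infants having their Day 1 sample on Day 7. The fitted change from Day 1 to Day 42 (log10) was:

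| Assumed fall (log10/week) | All pre-dose | Late samples, nominal time | Late samples, actual day |
|---|---|---|---|
| 0.10 | −0.528 | −0.505 | −0.534 |
| 0.25 | −1.319 | −1.261 | −1.335 |
| 0.50 | −2.638 | −2.523 | −2.670 |

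At 0.25 per week, nominal time understates the fall by 1.319 − 1.261 = 0.058 log10. Actual day does not understate it. For scale, the true change is −0.25 × 41/7 = −1.464, so the cubic's own misfit (1.464 − 1.319 = 0.145) is larger than the nominal-time effect.

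**6. Urine.** Section 4 schedules urine at Baseline and Months 4, 5 and 6. The mixed model in section 11.4.4 is described for whole blood and plasma only. No other scheduled urine viral-load sample before Month 4 could correct a late first one.

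**The case against.** The strongest reply is that the planned analysis is a curve over continuous time. A late sample entered at its actual day is then simply another point on the curve, and step 5 bears this out for blood. The analysis text also specifies no viral-load change score; where section 11.4.4 refers to baseline in the hearing model, it means baseline hearing. This stands as far as it goes. But the plan does not say that actual day is used, section 3.2.3 still names change as the outcome, the hearing model leaves its viral-load predictor undefined, and the model is not described for urine.

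It can also be said that most blood will be pre-dose in practice. The viral-load draw is listed with Day 1 hematology and chemistry, whose window closes on Day 1, and the neutrophil count must precede dosing. That is plausible, and it is why no share of infants affected can be asserted.

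A reader might infer more than the documents support:

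- *That change from baseline is understated as a matter of fact.* It depends on post-dose sampling, an early fall, and an analysis that treats the sample as Day 1. The only evidence on direction (section 2.1) is whole-blood load in symptomatic infants over 6 weeks, with no rate stated. Nothing is given for urine.
- *That baseline is taken after a full week of drug.* The most is six days.
- *That saliva outcomes are affected.* Section 3.2.3 lists no change in saliva viral load, and saliva is also collected before treatment for screening and confirmation.
- *That baseline resistance specimens are compromised.* The emergence outcome is set at Months 4, 5 and 6, and nothing suggests that six days of drug alters resistance status.
- *That one draw is meant to serve two visits.* Each visit separately calls for a sample; the plan only lacks a rule for the case where one draw fits both.

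**Conclusion.** The point holds in a limited form. The window, stated twice, permits an on-drug sample to act as baseline for whole blood, plasma and urine, and no other text prevents it. For infants sampled after the first dose, change can be understated if load falls early. The size is unknown, and the figures above only show how it scales with assumed rates and shares.

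The exposure is most direct for urine. For blood it arises with nominal visit time or a simple change score, and largely disappears if the mixed model uses actual sampling day. The primary hearing endpoint, the sample size and the safety outcomes are unaffected. Even within the hearing correlations, few events are expected: 3.18% of 176 is about 5.6 infants by 6 months, so sparse events are likely to limit that analysis more than this does. This is a minor point, worth settling before analysis so that the choice of baseline does not depend on the data.

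**What to change.** Add to section 11.4.4:

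- Baseline viral load is the last sample taken before the first dose.
- Samples taken after the first dose enter the mixed model at their actual study day and are never used as baseline in change or hearing-correlation analyses.
- A single blood draw on Days 5 to 7 is counted once, as an on-treatment sample.

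The collection window can stay as it is. The cost is a few lines in the analysis plan, plus the need to know, for a sample drawn on Day 1 itself, whether it came before the dose.

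The downside is that infants with no pre-dose sample leave the change-score analyses, although they remain in the blood mixed model. For urine the loss could be limited. Sections 4 and 7.1 require a confirmatory urine sample before treatment, and section 5.1 makes confirmation by urine PCR an entry criterion. If that sample is quantified, which the documents do not state, it could supply the baseline. The definition should then say that it counts even if collected before Day −3.
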